6.2 Safety Assessments

6.2.1 Vital Signs and Physical Measurements (Height and Weight)

Vital signs, body weight and height will be recorded at the scheduled visits as outlined in [Table 1](#) and [Table 2](#).

6.2.2 Electrocardiogram (ECG)

A standard 12-lead ECG will be recorded during the Screening Phase and at all scheduled visits as outlined in [Table 1](#) and [Table 2](#). A central ECG service will be utilized for reading all ECGs. The over read from the central ECG vendor should be used to determine eligibility for the study. The investigator will determine if any ECG abnormalities are clinically significant or not.

6.2.3 Physical Exam

Subjects will undergo a routine physical examination during the Screening Phase and at all scheduled visits as outlined in [Table 1](#) and [Table 2](#). Physical examinations to include examination of heart, abdomen and lungs, with review of any other system to be guided by symptoms.

6.2.4 Laboratory Assessments

6.2.4.1 Safety Laboratory Testing

Blood and urine samples will be obtained as outlined in [Table 1](#) and [Table 2](#) for clinical laboratory evaluations. A central laboratory vendor will be utilized for this study and a laboratory manual will be provided to each site. **If possible, subjects should be fasting for a minimum of 8 hours before laboratory tests.** However, if a subject is not fasting at a given visit, the blood draw should still be performed, and the non-fasting status should be documented.

1. Clinical safety labs:

Hematology: Hemoglobin, hematocrit, red blood cell count, white blood cell count with differential, and platelets;

Chemistry: Sodium, potassium, chloride, bicarbonate, calcium; glucose, HbA1c, BUN (urea), serum creatinine, uric acid, LDH, total protein, albumin, CPK (with local lab fractionation, if CK result is $> 5.0 \times \text{ULN}$).

eGFR using the estimated MDRD formula (calculated at central lab);

2. **LFTs:** AST, ALT, Alkaline Phosphatase and Bilirubin (Total, Direct, Indirect). Additional tests may be obtained to evaluate laboratory abnormalities and/or adverse events; please refer to the Laboratory manual.
3. **Lipid panel:** Cholesterol, LDL, HDL, triglycerides
4. **Urinalysis:** pH, specific gravity, ketones, nitrites, urobilinogen, leukocyte esterase, protein, glucose, and blood. If blood, protein or leukocytes are positive, reflex to microscopic examination.
5. **Urine Drug Screen:** For drugs of abuse
6. **FSH:** For WOCBP at screening, to determine WOCBP status

Additional tests may be obtained to evaluate laboratory abnormalities and/or adverse events; please refer to the Laboratory Manual.

6.2.4.2 Pregnancy Testing

WOCBP will complete pregnancy tests (serum and / or urine) at specified study visits, prior to taking study medication, and as outlined in [Table 1](#).

6.2.5 Sheehan Suicidality Tracking Scale

The Sheehan STS (S-STTS) is a prospective, subject-reported or clinician-administered rating scale that contains 16 questions to track both treatment-emergent suicidal ideation and behaviors.^{10,11} The S-STTS will be completed on a paper form at the site. At the screening visit, the recall period for completing the S-STTS is 30 days prior; at all other visits, the recall period for completing the S-STTS is since the last visit. Any responses other than 0 must be immediately evaluated by the investigator. If the investigator determines that a subject is at risk of suicide or self-harm, appropriate measures to ensure the subject's safety and obtain mental health evaluation must be implemented. In such circumstances, the subject must immediately be discontinued from the study. The event should be recorded as either an AE or SAE as determined by the investigator and reported within 24 hours to the Sponsor. Any subject with a response greater than 0 to any question, excluding Question 2, must be immediately discontinued from the study. Subjects with a response of 1 ("a little") to Question 2 will be discontinued per the investigator's assessment or if the response persists. Subjects with a response greater than 1 on Question 2 will be discontinued from the study immediately.

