4.3 Schedule of Assessments

Table 1. Schedule of Assessments – Double-Blind Treatment Phase^{9, 10}

Procedure	Screening Visit	Observation Period ¹⁰ (28 days, + 3 days)	Pre-Randomization Laboratory Visit: must occur within 96 hours of Baseline (Randomization) Visit ¹¹	Baseline (Randomization) Visit (Day 1)	Week 2 (Day 14 +/- 2 days)	Week 4 (Day 28 +3 days)	Weeks 8 (Day 56) and 12 (Day 84) (all visits + 3 days)
Eligibility Assessments							
Informed Consent	X						
	X						
Inclusion/Exclusion Criteria	X			X			
Medical History	X						
Migraine History (signs/symptoms/prior treatment/frequency/intensity)	X						
Rescue Medication paper diary, Concomitant Medication paper diary and Menstrual Period paper log (female subjects) ¹	X	X	X	X	X	X	X
Randomize subject / IWRS ²				X			
Safety Assessments							
Physical Examination	X			X		X	X
Vital Signs / Physical Measurements ³	X			X		X	X

Procedure	Screening Visit	Observation Period¹⁰ (28 days, + 3 days)	Pre-Randomization Laboratory Visit: must occur within 96 hours of Baseline (Randomization) Visit ¹¹	Baseline (Randomization) Visit (Day 1)	Week 2 (Day 14 +/- 2 days)	Week 4 (Day 28 +3 days)	Weeks 8 (Day 56) and 12 (Day 84) (all visits + 3 days)
Clinical Safety Laboratory Testing	X			X		X	X
Liver Function Test (LFTs)	X		X	X	X	X	X
Lipid Panel				X			
ECG	X			X		X	
Urinalysis				X			
Urine Drug Screen for drugs of abuse	X						
FSH, if applicable, to determine WOCBP status	X						
Pregnancy Test	X (urine)		X (serum)	X (urine)		X (urine)	X (urine)
AE, SAE, and Concomitant Procedure assessment ⁴	X		X	X	X	X	X
Sheehan Suicidality Tracking Scale	X			X	X	X	X
Clinical Drug Supplies / Study Supplies							
Dispense Study Medication ⁵				X		X	X
Administer study medication ⁶					X	X	X
Electronic Diary (eDiary) dispensed	X						

Procedure	Screening Visit	Observation Period¹⁰ (28 days, + 3 days)	Pre-Randomization Laboratory Visit: must occur within 96 hours of Baseline (Randomization) Visit ¹¹	Baseline (Randomization) Visit (Day 1)	Week 2 (Day 14 +/- 2 days)	Week 4 (Day 28 +3 days)	Weeks 8 (Day 56) and 12 (Day 84) (all visits + 3 days)
Enter use of study medication in eDiary				X	X	X	X
Return unused study medication to site for compliance check					X	X	X
eDiary returned / reviewed for completeness ⁷		X	X	X	X	X	X
Other Assessments							
Daily report of migraine occurrence and severity reported by subject in eDiary ⁸		X	X	X	X	X	X
Migraine-Specific Quality-of-Life Questionnaire (MSQ) v 2.1				X			X (week 12 only)

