Procedure	Phone visit to confirm eligibility based on laboratory criteria¹	Week 14 (Day 98 ± 3 days)	Week 16 (Day 112) and 20 (Day 140) (±3 days)	Visits every 4 weeks Week 24 (Day 168) to Week 64 (Day 448) / EOT (±3 days)	2-Week Follow-up Safety Visit (14 days after EOT visit ± 2 days)	8-Week Follow-up Safety Visit (8 weeks (-2 days to +14 days) after EOT visit)
AE, SAE, and Concomitant Procedure Assessment ⁵		X	X	X	X	X ⁵
Sheehan Suicidality Tracking Scale		X	X	X	X	
Clinical Drug Supplies / Study Supplies						
Dispense Study Medication ^{1, 6}			X	X-all visits except Week 64 / EOT		
Administer Study Medication ⁷		X	X	X		
Enter Use of Study Medication in eDiary		X	X	X		
Return unused study medication to site for compliance check		X	X	X		
eDiary returned/reviewed for completeness ⁸		X	X	X		
Other Assessments						
Daily report of migraine occurrence and severity reported by subject in eDiary ⁹		X	X	X		
Migraine-Specific Quality-of-Life Questionnaire (MSQ) v 2.1				X (Weeks 24 and 64 only)		

Procedure	Phone visit to confirm eligibility based on laboratory criteria ¹	Week 14 (Day 98 ± 3 days)	Week 16 (Day 112) and 20 (Day 140) (±3 days)	Visits every 4 weeks Week 24 (Day 168) to Week 64 (Day 448) / EOT (±3 days)	2-Week Follow-up Safety Visit (14 days after EOT visit ± 2 days)	8-Week Follow-up Safety Visit (8 weeks (-2 days to +14 days) after EOT visit)
Migraine Disability Assessment (MIDAS)				X (Weeks 24 and 64 only)		

¹ Study eligibility must be confirmed by Week 12 laboratory results prior to first dose of study medication, which is dispensed at the Week 12 visit. Sites must contact subject by phone to confirm study eligibility prior to subject taking first dose.

² Concomitant medications, including prophylactic and rescue medications, taken during the Open-label, Extension Phase should be recorded in the subject’s paper diary and reviewed by study personnel at each visit. Female subjects will also record menstrual period information on the paper log which should be reviewed by study personnel at each visit.

³ Collect if treatment with concomitant medication is required for an AE or if concomitant medication is considered related to AE.

⁴ Weight, body temperature, respiratory rate, blood pressure, and heart rate will be collected at all timepoints where indicated. Sitting arterial systolic and diastolic blood pressure and radial artery pulse rate will be measured.

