4.3.1.1 Pre-Randomization (Laboratory) Visit

Within 96 hours +48 hours (4 days +2 days) of the Randomization Visit, subjects must return to the study site for the Pre-Randomization (Laboratory) Visit. This visit occurs within the Observation Period. Safety labs and a serum pregnancy test for WOCBP will be obtained and compliance with the eDiary will be assessed. If the subject continues to meet study entry criteria and laboratory test results are acceptable per protocol, the subject will be randomized at the Baseline Visit into the double-blind treatment phase. If the laboratory results are not acceptable per protocol, the subject is determined to be a Screen Failure and must return to the study site to return the eDiary. Repeat testing because of liver function test (LFT) abnormalities will not be permitted.

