Due to the COVID-19 Pandemic, visits may be conducted remotely (ex: telephone, telemedicine) and must be documented within the source records as being conducted remotely. All procedures not able to be completed due to a visit being conducted remotely must be reported as a protocol deviation and can be performed at the next visit, where appropriate to do so based on subject presentation.

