 - f) Score of > 0 on the Sheehan Suicidality Tracking Scale (See Section 6.2.5) for the period of 30 days prior to screening.
 - g) Previous enrollment in any multiple dose BHV3000 (rimegepant) study, such as BHV3000-201, regardless of the number of doses taken. Subjects may be considered for BHV3000-305 if the subject participated in any of the following single dose studies: BHV3000-301, BHV3000-302, or BHV3000-303, but did not participate in any multiple dose rimegepant study. Note that subjects who were considered screen failures in a past BHV3000 study may be considered after discussion with the Sponsor and written approval is received. Subjects who were considered screen failures from BHV3000-305 may be considered for re-screening provided the ineligibility was due to one of the eligibility items adjusted in Amendment 03 (Protocol Version 04): exceeded number of headache days (previously greater than 13) or didn't meet number eDiary entries during Observation Period (previously at least 26). Subjects may also be considered for re-screening provided the ineligibility was due to the eligibility item adjusted in Amendment 04 (Protocol Version 05): BMI less than 33.0 kg/m² (previously BMI less than or equal to 30kg/m²). Subjects who were considered screen failures from BHV3000-305 for other reasons should be discussed with the Sponsor and approval must be granted prior to considering for re-screening. Adequate documentation in source records must support the previously failed criteria.
 - h) Subjects are excluded if they have had no therapeutic response with > 2 of the 8 medication categories for prophylactic treatment of migraine listed in Appendix 4 after an adequate therapeutic trial. Additional details can be found in Section 15.4 Appendix 4.
 - i) Participation in any other investigational clinical trial while participating in this clinical trial. Subjects with an exclusionary match found in the CTS Database will be excluded.
 - j) Past participation in a clinical trial within 30 days prior to the Screening Visit. Note: Subjects who were considered screen failures within the last 30 days should not be considered as excluded.
-

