### **6.5.5 Sheehan-Suicidality Tracking Scale**

The S-STIS is a prospective rating scale that contains 16 patient-reported questions and 6 clinician-reported questions to track both treatment-emergent suicidal ideation and behaviors. The S-STIS will be assessed at early termination and the following visits: screening; baseline; Weeks 2, 4, 8, and 12 of the DBT phase; Weeks 14, 16, and every 4 weeks through Week 64 of the OLE phase; and follow-up Weeks 2 and 8.

S-STIS scores are calculated as described in the BHV3000 Core SAP.

Values and changes from baseline in the self-reported S-STIS ideation subscale, behavior subscale, and total score will be summarized as continuous parameters at baseline and the worst (highest) score in safety analysis periods by treatment group and overall.

In addition, the number and percentage of subjects in the worst (highest) score change from baseline category (i.e.,  $< -1$ ,  $-1$ , no change,  $1$ ,  $> 1$ ) in safety analysis periods will also be presented by treatment group and overall for the ideation subscale, behavior subscale, and total score.

S-STIS scores, worst score changes from baseline, and worst score change categories from baseline will be summarized for the following safety analysis periods and populations: (1) on-DBT for treated subjects; (2) on-DB or OL rimegepant for DB or OL rimegepant treated subjects, using DB or OL rimegepant baseline instead of baseline; and (3) follow-up for follow-up subjects.

A by-subject listing of the S-STIS will be provided for enrolled subjects. Refer to the BHV3000 Core SAP for the listing content.

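### The S-STS recall runs from the last visit, not the last S-STS, so read literally the Baseline form covers at most 4 to 6 days of the Observation Period

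*Protocol*

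**What the plan says.** Protocol Section 6.2.5 fixes two recall rules. "At the screening visit, the recall period for completing the S-STTS is 30 days prior"; after that, "at all other visits, the recall period for completing the S-STTS is since the last visit". It does not say whether the last visit means any visit or the last one at which the scale was completed. The form is on paper at the site, and the scale may be subject-reported or clinician-administered.

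Table 1 in Protocol Section 4.3 schedules the S-STS at Screening, Baseline and Weeks 2, 4, 8 and 12. The cell for the Pre-Randomization Laboratory Visit is empty. SAP Section 6.5.5 agrees: "screening; baseline; Weeks 2, 4, 8, and 12 of the DBT phase".

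Protocol Section 4.1 lists the laboratory visit among the study visits. Section 4.3.1.1 requires a return to the site for it and adds: "This visit occurs within the Observation Period". Table 1 footnote 11 puts it 4 days before randomization, or up to 6 for scheduling convenience.

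In the open-label phase, Table 2 has a column headed "Phone visit to confirm eligibility based on laboratory criteria" with no S-STS. Section 4.3.3 adds that, because of COVID-19, "visits may be conducted remotely (ex: telephone, telemedicine) and must be documented within the source records as being conducted remotely". Procedures that cannot be done remotely are protocol deviations and can be performed at the next visit.

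**The concern.** The recall is tied to a visit, while the scale is given only at some visits. Wherever a visit without an S-STS sits between two visits with one, a site following the words will shorten the later recall and leave the earlier days unasked. The laboratory visit does this just before randomization, and every randomized subject is scheduled to have it.

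Two things are at stake. First, Section 6.2.5 makes prompt evaluation and discontinuation depend on S-STS answers, and those rules cannot act on days that no form asks about. Secondly, SAP Section 6.5.5 summarizes change from baseline to the worst score in each period. A baseline with a recall of a few days would be compared with on-treatment forms whose nominal recall is 14 or 28 days.

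**Working it through.** The plan states no figure for S-STS coverage, so there is none to reproduce. The check compares the recall rule with the visit schedule and counts days.

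**Inputs**
- Observation Period length *L*: 28 days, or 31 with the +3 day window (Table 1 and footnote 7).
- Days from laboratory visit to Baseline *w*: at most 4, or 6 with the allowance (Sections 4.1 and 4.3.1.1; Table 1 footnote 11). These are upper limits, so *w* can be smaller.
- Screening recall: the 30 days before Screening, so it ends where the Observation Period begins.
- Assumption: the Observation Period starts directly after Screening and runs to Baseline.

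**Literal reading.** The Baseline form covers *w* days, so uncovered days = *L* − *w*, and the share is (*L* − *w*)/*L*.

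| *L* | *w* | Uncovered days | Share |
|---|---|---|---|
| 28 | 6 | 28 − 6 = 22 | 22/28 = 78.6% |
| 28 | 4 | 28 − 4 = 24 | 24/28 = 85.7% |
| 28 | 1 (assumed) | 28 − 1 = 27 | 27/28 = 96.4% |
| 31 | 6 | 31 − 6 = 25 | 25/31 = 80.6% |
| 31 | 4 | 31 − 4 = 27 | 27/31 = 87.1% |

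Because *w* cannot exceed 6, the minimum gap is 22 of 28 days, or 25 of 31.

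**Alternative reading.** If the last visit means the last one with an S-STS, the Baseline form reaches back to Screening and the gap is 0 days.

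**Other places where the rule can bite**
- *Phone contact after Week 12.* Its date is not stated. If it counts as a visit, it could shorten the nominal 14-day Week 14 recall by anything from 0 to about 14 days.
- *Unscheduled dispensing visits* (Table 1 footnote 5, Table 2 footnote 6). The mechanism is the same, but no frequency is given.
- *Remote visits in the open-label phase.* If the on-site paper S-STS is not done and is caught up at the next visit with the literal recall, the interval before the remote visit is lost. Nominally that is 14 days for Weeks 14 and 16 (98 − 84 and 112 − 98) and 28 days for Weeks 20 to 64.
- *Follow-up.* Table 2 has an S-STS at the 2-Week Follow-up but not at the 8-Week Follow-up, whereas SAP Section 6.5.5 lists follow-up Weeks 2 and 8. Under Table 2, nominally 56 − 14 = 42 days at the end of follow-up have no S-STS (54 − 16 = 38 to 70 − 12 = 58 with the visit windows).

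**Baseline reference.** SAP Section 6.2.5 takes the last non-missing value on or before study drug start, normally the Baseline form. In the double-blind table any shortening affects both arms alike. In the combined double-blind or open-label rimegepant table, subjects first given placebo take their baseline at open-label start, normally the Week 12 form with a nominal 28-day recall. On the literal reading that table mixes two recall lengths.

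**The case against.** The strongest reply is that the sentence in Section 6.2.5 concerns visits at which the S-STS is completed. Its reference to all other visits cannot include the laboratory visit, because Table 1 has no S-STS there. Carry that meaning through the sentence and the Baseline form reaches back to Screening, with no gap. The printed S-STS forms are not in the documents and may settle the matter. This stands as a fair alternative reading, and it is why the gap cannot be called certain. It does not remove the point: the term is undefined, the laboratory visit is listed as a study visit, and sites may differ.

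Other points that stand:
- Exclusion 7f is unaffected. It applies to a "Score of > 0 on the Sheehan Suicidality Tracking Scale (See Section 6.2.5) for the period of 30 days prior to screening", which the Screening form covers in full.
- AE and SAE assessment is marked at both the laboratory visit and Baseline, and the SAP tabulates suicidality AEs, including before treatment. Events therefore have another reporting route. It is not a structured screen, since Protocol Section 8 tells sites not to question subjects about specific AEs.
- The effect on scores is probably small. A Screening score above 0 excludes, and under Section 6.2.5 most later responses above 0 lead to discontinuation, so baseline scores should be near zero on either recall.

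A reader might infer that each interval before a remote visit goes unscreened. The documents do not support that. Remote visits are a COVID-19 allowance in the open-label and follow-up schedule, the scale may be clinician-administered, and missed procedures can be done later. The loss arises only if the form is skipped and then caught up with the literal recall.

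**Conclusion.** The point holds as a defect in the wording of a stated rule. Followed literally, it leaves at least 22 of 28 Observation Period days (79% or more), or at least 25 of 31, outside both the Screening and the Baseline recalls. Read as the last S-STS visit, it leaves none. Coverage before randomization and the baseline reference in SAP Section 6.5.5 therefore depend on how a site interprets one term.

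A reader might go further and conclude that most of the Observation Period is never screened in any randomized subject. The schedule allows that outcome but does not establish it. Nor is there a basis for claiming bias between arms in the double-blind table, or for putting a size on any shift in scores. The count rests on the laboratory visit being treated as the last visit and on the Observation Period running from Screening to Baseline. This is a cheap improvement, not a threat to the trial's conclusions.

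**What to change.** 1. In Protocol Section 6.2.5, make the recall at every visit after Screening run from the last completed S-STS, and record the date of that S-STS on the form.
2. State how the S-STS is handled at remote visits. If it is to be given by telephone or video, that is an added procedure and needs its own short instruction.
3. Reconcile Table 2, which has no S-STS at the 8-Week Follow-up, with SAP Section 6.5.5, which lists one.

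The discontinuation rules are unchanged and no visit is added. The first change costs one sentence and a form header; the other two need a brief clarification each. On the literal reading, the uncovered part of the Observation Period falls from 22 to 27 days, for a laboratory visit 4 to 6 days before Baseline, to zero.

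The downside is a longer recall: about 4 weeks at Baseline, in line with the 28-day intervals later in the study, and up to about 8 weeks after a single missed S-STS (28 + 28 = 56 days at nominal visit days).

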6.3 Efficacy Assessments

The eDiary will be used daily to record rescue medication dosing occurrences (i.e., with triptans, ergotamine, or other), and migraine occurrence, characteristics, and severity during the observation period, double-blind treatment phase, and open-label extension phase.

Efficacy assessments will be derived from eDiary data, and will include the number of migraine days by severity (total; moderate or severe) per month, number of rescue medication days per month, and MRM days per month, in each month by study period.

6.4 Other Assessments

6.4.1 Migraine-Specific Quality-of-Life Questionnaire v 2.1

Impact of treatment on subject-reported quality of life will be assessed using the Migraine-Specific Quality-of-Life Questionnaire version 2.1 (MSQ v 2.1). The MSQ v 2.1 is a 14-item instrument that has been validated in 3 domains: role function - restrictive, role function - preventive, and emotional function.¹²

[REDACTED]

[REDACTED]

6.4.4 Migraine Disability Assessment (MIDAS) Questionnaire

The Migraine Disability Assessment (MIDAS) is a retrospective, subject-reported, 5-item questionnaire that measures headache-related disability as lost days due to headache from paid work or school, household work and non-work activities over a 3-month period. The MIDAS will be completed on a paper form at the site.¹³

[REDACTED]

